3.4. Treatments Administered

For the Double-blind Treatment Period, a fixed dose (determined at Visit 2) of trifarotene cream HE1 100 µg/g or 200 µg/g or vehicle cream will be applied topically twice weekly on up to 90% body surface area (BSA) of each subject. Trifarotene cream HE1 is a cream containing 100 or 200 µg/g (0.01% [w/w] or 0.02% [w/w], respectively) of CD5789. Vehicle contains the same ingredients, without the CD5789. Trifarotene cream HE1 and vehicle will be provided in cream form for topical application and will be packaged in 50-g tubes from which up to 36 g of investigational product (IP) may be dispensed per application, i.e., the maximum dose per

application. Study staff will apply the first dose of study drug to each subject in the clinic on Day 1 after baseline measurements, and will record the amount of study drug applied.

Thereafter, each subject will apply approximately the same amount (up to 36 g) of study drug as for the first dose on up to 90% of BSA twice weekly, sparing the scalp, inguinal, and axillary areas. Subjects will receive an adequate number of tubes to use 1 tube per application and will use a new tube for each treatment day.

For the OLE, all subjects will receive trifarotene cream HE1 200 µg/g and apply the same fixed dose in the same manner as in the Double-blind Period for an additional 90 days.

If the treatment causes application site reactions, the frequency of application will be reduced or interrupted only on the area of concern, as indicated herein. During all clinic visits, the investigator will assess local tolerability (Scale: 0-3 [none, mild, moderate, severe]) for stinging/burning, pruritus, erythema) for each body area (chest/abdomen, back, arms, legs, and face/neck), and the following procedures will be followed:

- If a score of 2 (moderate) is recorded on a local tolerability assessment scale (stinging/burning, pruritus, erythema) on any treated area, the study drug will be applied on that area only once weekly, until the score is back to <2. Continue to treat all other areas twice weekly provided the score is <2 on those areas.
- If a score of 3 (severe) is recorded on a local tolerability assessment scale (stinging/burning, pruritus, erythema) on any treated area, the study drug will not be applied on that area until the score is back to <3 (i.e., “drug holiday”). Continue to treat all other areas twice weekly provided the score is <2 on those areas.

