- o. Study staff will apply initial dose of study drug in the clinic after Baseline measurements, and the amount of study drug used will be measured (i.e., 36-g tube will be measured before and after application to determine amount used).
- p. Study drug provided in 50-g tubes (maximum single application is 36 g). Measure study drug kits (tubes and box, but not leaflets) before dispensing; subjects must record days/times of study drug application in the diaries and any areas of skin not treated, e.g., due to local reactions. Dispense enough additional study drug until next visit (except at Day 90, unless subject consents to continue into OLE).

- q. Confirm study drug compliance by weighing the studykits (tubes and boxes, but not leaflets) and reviewing diary.

Table 2: Schedule of Events for Open-label Extension

	Open-label Treatment Period ^a						Follow-up
	Telephone Visit (Day 97) ^a	Day 104 ± 5 days	Day 120 ± 7 days	Telephone Visit (Day 134)	Day 150 ± 7 days	Day 180 ± 7 days/ET	Day 194 or 14 days after End of Open-label Treatment
Visit		7 ^a	8 ^a		9 ^a	10 ^a	11 ^a
Informed consent ^b							
Physical examination ^c						X	X
Vital signs (blood pressure and pulse)			X	X	X	X	X
Record IGA ^d		X	X		X	X	X
VIIS ^e assessment		X	X		X	X	X
Roughness assessment ^f		X	X		X	X	X
Palm/sole assessment		X	X		X	X	X
Palm/sole fissuring assessment		X	X		X	X	X
Ectropion score		X	X		X	X	X
Clinical laboratory tests (hematology, chemistry, urinalysis) ^g			X			X	
Pregnancy test for female subjects (urine) ^h			X		X	X	X
Coagulation panel			X			X	
12-lead ECG			X			X	
PK blood sample collection ⁱ			X			X	
Application instructions, advice on emollient and sunscreen use ^j	X	X	X	X			
Dispense study drug and diaries ^k		X	X		X		
Concomitant medications	X	X	X	X	X	X	X

	Open-label Treatment Period ^a						Follow-up
	Telephone Visit (Day 97) ^a	Day 104 ± 5 days	Day 120 ± 7 days	Telephone Visit (Day 134)	Day 150 ± 7 days	Day 180 ± 7 days/ET	Day 194 or 14 days after End of Open-label Treatment
Visit		7^a	8^a		9^a	10^a	11^a
Tolerability assessment		X	X		X	X	
Adverse events (and review diaries)	X	X	X	X	X	X	X
Collect all used/unused study drug ¹		X	X		X	X	

Abbreviations: ECG = electrocardiogram; ET = early termination; HEENT = head, eyes, ears, nose, throat; ICF = informed consent form; IGA = Investigator's Global Assessment; PK = pharmacokinetic; OLE = open-label extension; VIIS = Visual Index for Ichthyosis Severity; WOCBP = women of childbearing potential

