6.1.7. Derived Variables

- IGA average score = in protocol version 1.0, IGA was assessed by body area (chest/abdomen, back, arms, and legs). Under protocol version 2.0, this was changed to a global (overall) assessment. For comparability, the average of the body area IGA results will be taken to yield one score for subjects enrolled under protocol version 1.0. Scores will range from 0 to 4. Higher scores indicate worse disease.
- VIIS total score = sum of the individual body area scaling scores, with a range of 0 to 16. Each individual item is scored on a scale of 0-4, where 0 = normal skin; no perceptible scale or smoothening and 4 = confluent, primarily large, thick scales. Higher scores indicate worse scaling.
- Ectropion total score = sum of the 8 individual item scores (lateral apposition, medial apposition, scleral show, conjunctival show, excess tear film, redness of the eye, round canthus, punctum lacrimale), with a range of 0 to 8. Each individual item is scored 0

(nonaffected/no/invisible), 0.5 (≤ 1 mm/emerging), or 1 (affected/yes/visible). Higher scores indicates worse ectropion.

- DLQI total score = sum of the 10 individual item scores, with a range of 0 to 30. Higher scores indicate poorer quality of life.
- CDLQI total score = sum of the 10 individual item scores, with a range of 0 to 30. Higher scores indicate poorer quality of life.
- Number of doses taken = total number of tubes returned – total number of tubes returned unused
- Number of weeks on study = (last day on study – treatment start date + 1) / 7
- Number of expected doses = 2 * number of weeks on study
- Total weight used = total weight of tubes dispensed (grams) – total weight of tubes returned (grams)
- Initial application amount used = tube weight before drug application (grams) – tube weight after drug application (grams), as collected on the initial study drug application CRF
- Compliance by tube weight = total weight used / total weight of tubes dispensed * 100%
- Compliance by number of doses = number of doses taken / number of expected doses * 100%
- Change from baseline = value at current time point – value at baseline.
- TEAE = An AE is defined as treatment emergent if the onset or worsening is at the time of or following the start of the first application of study drug (trifarotene or vehicle) through the Follow-up Visit or Early Termination Visit, whichever occurs first..

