7.4. Exposure and Compliance

Compliance by tube weight and compliance by number of doses will be summarized by treatment group using descriptive statistics. The total weight of tubes dispensed and returned, as well as total number of tubes dispensed, returned, and returned unused will also be summarized. This analysis will be conducted for the Safety population and for the OLE Safety population.

A subject is compliant with study product if he or she takes at least 80%-120% of the scheduled doses as assessed by number of doses taken reported, supplemented by tube weight and diary entries. The number and percentage of subjects who were compliant will be tabulated by treatment group for the Double-blind Period and overall for the OLE. Derivations of compliance are defined in Section 6.1.7.

All initial study drug application, drug accountability (dispensed and returned), and subject diary data collected will be listed. Changes in treatment administration or treatment dispensation due to COVID-19 including start and end dates of change, method of alternative administration/dispensation, dosing interruptions, and relevant changes to compliance expectations (weights or tube counts) will be documented from the COVID-19 visit impact log.

8. Efficacy Analysis

All efficacy endpoints will be summarized using the ITT population. The primary analysis will be repeated in the mITT and PP populations.

Summaries of efficacy variables in the OLE will be provided using the OLE ITT. Primary IGA summaries will also be provided for the OLE mITT and OLE PP populations. For continuous efficacy analyses using MMRM, only formal comparisons of change from baseline will be performed in the OLE. No other formal inferential analyses will be conducted for efficacy variables in the OLE.

All efficacy data, regardless of population, will be presented in data listings.

If alternative methods are used for capturing efficacy assessments (i.e., in person not on site at the subject's home, remotely with visual aid, or remotely via telephone), additional sensitivity or subgroup analyses may be performed to assess the potential impact to efficacy analyses. These will be delineated as ad hoc analyses in the CSR.

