Min, Max	XX, XX	XX, XX	XX, XX	XX, XX

Abbreviation: OLE = open label extension. SD = standard deviation.

Note: Subjects are summarized by actual treatment group. Subjects were randomized to either Trifarotene cream HE1 100 ug/g, Trifarotene cream HE1 200 ug/g, or vehicle in the Double-blind period. All subjects received Trifarotene cream HE1 200 ug/g in the OLE.

SOURCE: Listings 16.2.5.1, 16.2.5.2, 16.2.5.3

Programming note: Continue for Day 30, Day 60, and Day 90.

Table 14.1.5.2
Summary of Drug Accountability (Drug Returned and Dispensed)
OLE Safety Population

Same shell as Table 14.1.5.1

Programming note: Only include one column for Trifarotene cream HE1 200 ug/g.

Continue for Day 104, Day 120, Day 150 and Day 180.

Update Note: to read "Note: Subjects are summarized by treatment group. All subjects received Trifarotene cream HE1 200 ug/g in the OLE."

Table 14.1.5.3
Summary of Treatment Exposure and Compliance
Safety Population

Variable Statistic or Category	Trifarotene cream HE1 100 ug/g (N=XX)	Trifarotene cream HE1 200 ug/g (N=XX)	Vehicle (N=XX)	Overall (N=XX)
Compliance by Tube Weight (%) [1]				
n	XX	XX	XX	XX
Mean (SD)	XX.X (XX.XX)	XX.X (XX.XX)	XX.X (XX.XX)	XX.X (XX.XX)
Median	XX.X	XX.X	XX.X	XX.X
Min, Max	XX, XX	XX, XX	XX, XX	XX, XX
Compliant	XX (XX.X%)	XX (XX.X%)	XX (XX.X%)	XX (XX.X%)
Not Compliant	XX (XX.X%)	XX (XX.X%)	XX (XX.X%)	XX (XX.X%)
Compliance by Number of Doses (%) [2]				
n	XX	XX	XX	XX
Mean (SD)	XX.X (XX.XX)	XX.X (XX.XX)	XX.X (XX.XX)	XX.X (XX.XX)
Median	XX.X	XX.X	XX.X	XX.X
Min, Max	XX, XX	XX, XX	XX, XX	XX, XX
Compliant	XX (XX.X%)	XX (XX.X%)	XX (XX.X%)	XX (XX.X%)
Not Compliant	XX (XX.X%)	XX (XX.X%)	XX (XX.X%)	XX (XX.X%)

Abbreviation: SD = standard deviation.

Note: Percentages are n/Number of subjects in the Safety population within actual treatment group and overall*100. A subject is compliant with study product if he or she takes at least 80%-120% of the scheduled doses as assessed by diary entries, supplemented by tube weight.

[1] Compliance by tube weight = total weight used / total weight of tubes dispensed *100%, where total weight used = total weight of tubes dispensed (grams) – total weight of tubes returned (grams)

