[2] Compliance by number of doses = number of doses taken / number of expected doses * 100%, where number of doses taken = total number of tubes dispensed – total number of tubes returned – total number of tubes returned unused, number of expected doses = 2 * number of weeks on study, and number of weeks on study = (last day on study – treatment start date + 1) / 7

SOURCE: Listings 16.2.5.1, 16.2.5.2, 16.2.5.3

Table 14.1.5.4
Summary of Treatment Exposure and Compliance
OLE Safety Population

Same shell as Table 14.1.5.3

Programming note: Only include one column for Trifarotene cream HE1 200 ug/g.

Update Note: to read "Note: Percentages are n/Number of subjects in the OLE Safety population within treatment group and overall*100. All subjects received Trifarotene cream HE1 200 ug/g in the OLE."

Add OLE = open label extension to Abbreviations.

Table 14.2.1.1.1
Primary Analysis: Logistic Regression Analysis of Successful Resolution of LI
ITT Population

Study Visit Statistic	Trifarotene cream HE1 100 ug/g (N = XX)	Trifarotene cream HE1 200 ug/g (N = XX)	Overall Trifarotene cream HE1 (N = XX)	Vehicle (N = XX)
Day 90 n [1] Successful Resolution [2]	XX XX (XX.X%)	XX XX (XX.X%)	XX XX (XX.X%)	XX XX (XX.X%)
Odds Ratio (Trifarotene cream HE1 vs Vehicle)	X.XX	X.XX	X.XX	
95% CI for Odds Ratio	(X.XX, X.XX)	(X.XX, X.XX)	(X.XX, X.XX)	
P value [3]	X.XXX	X.XXX	X.XXX	
Difference in Proportion (Trifarotene cream HE1 vs Vehicle)	X.XX	X.XX	X.XX	
95% CI for Proportion Difference	(X.XX, X.XX)	(X.XX, X.XX)	(X.XX, X.XX)	
P value [3]	X.XXX	X.XXX	X.XXX	

Abbreviation: CI = confidence interval; EOT = end of treatment; IGA = Investigator's Global Assessment; ITT = intent to treat; LI = Lamellar Ichthyosis; OR = odds ratio.
Note: Percentages are n/Number of subjects in the ITT population within randomized treatment group*100. The 5-point (0 - 4) IGA is a measure of disease severity which considers both scaling and roughness. Higher IGA scores represent more severe disease.

[1] Number of subjects with an IGA assessment at each visit.

[2] Number of subjects with successful resolution of LI at a visit. Successful resolution is defined as clear/almost clear overall (IGA of 0 or 1, respectively) and at least a 2-grade change from Baseline on the 5-point (0 - 4) IGA scale. Baseline is defined as the last non-missing assessment recorded prior to the first dose of treatment in the Double-blind Period.

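### Tube-weight compliance is divided by dispensed weight, so a fully adherent subject scores at most 72% against an 80%-120% rule, and the exposure table's dose-count footnote contradicts Section 6.1.7

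*SAP*

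**What the plan says.** **Weight measure.** Section 6.1.7 of the SAP gives "Compliance by tube weight = total weight used / total weight of tubes dispensed * 100", where weight used is weight dispensed minus weight returned. Footnote [1] of Table 14.1.5.3 repeats this.

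**Supply.** Section 3.4 describes study drug "packaged in 50-g tubes from which up to 36 g of investigational product (IP) may be dispensed per application", with a new tube for each treatment day. The schedules of events have used and unused drug collected, and kits weighed with their boxes.

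**Dose measure.** Section 6.1.7 starts from "Number of doses taken = total number of tubes returned" and subtracts tubes returned unused. Footnote [2] of Table 14.1.5.3 reads "where number of doses taken = total number of tubes dispensed" and then subtracts both tubes returned and tubes returned unused. Expected doses are twice the number of weeks on study.

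**Classification.** Under Section 7.4 a subject is compliant if he or she "takes at least 80%-120% of the scheduled doses as assessed by number of doses taken reported", with tube weight and diary as supplements. The note to Table 14.1.5.3 has compliance "as assessed by diary entries, supplemented by tube weight". The shell prints Compliant and Not Compliant rows under both measures.

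**Use.** Section 5 makes compliance a condition for the PP and OLE PP populations.

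**The concern.** A compliance percentage should compare what was used with what should have been used. The weight formula compares it with what was handed out, and each tube holds more than may be applied from it. The score is therefore low by design and cannot be read against 80%-120%.

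The table that reports compliance also carries a dose formula different from the one in the text. The basis of the flag differs between text and table, and neither place says how a supplementary measure is to be combined with the main one.

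At stake are the accuracy of the exposure table and an unambiguous rule for per-protocol membership, which Section 5 requires to be settled before database lock.

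**Working it through.** The plan states no compliance result to reproduce. The check applies its formulas to one fully adherent subject.

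**Inputs**
- Tube content 50 g, at most 36 g per application, one new tube each time (Section 3.4).
- Used and unused tubes all returned (schedule of events).
- Expected doses over 90 days: 2 x 90/7 = 25.71 (Section 6.1.7). The subject is taken to make 26 applications.

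**1. Compliance by tube weight**, (dispensed - returned)/dispensed:
- 36 g per application: (26 x 36)/(26 x 50) = 936/1300 = 72.0%.
- 30 g: 30/50 = 60.0%. 20 g: 20/50 = 40.0%.
- 36 g with four unused spare tubes: 936/(30 x 50) = 62.4%.
- 36 g with packaging in the weights, assuming 5 to 20 g per tube because the plan gives no figure: 36/55 = 65.5% down to 36/70 = 51.4%.
- Grams per tube needed for 80%: 0.8 x 50 = 40 g, if all tubes are returned.

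**2. Effect of unreturned tubes.** A tube not returned counts as fully used. With 8 of 26 used tubes missing and 36 g per application, 18 return with 14 g each: (1300 - 18 x 14)/1300 = 1048/1300 = 80.6%. The Section 6.1.7 dose count for the same subject falls to 18/25.71 = 70.0%. The two measures move in opposite directions.

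**3. Doses taken** (D dispensed, R returned, U returned unused), all tubes returned so R = D:

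| Tubes dispensed | Unused | Section 6.1.7: R - U | Footnote [2]: D - R - U |
|---|---|---|---|
| 26 | 0 | 26 (101.1%) | 0 (0%) |
| 28 | 2 | 26 (101.1%) | -2 (-7.8%) |
| 30 | 4 | 26 (101.1%) | -4 (-15.6%) |

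With everything returned, the footnote reduces to -U. If returned is read as used tubes only, it gives 0.

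**4. Basis of the flag.** Section 7.4 puts the dose count first and lets weight and diary supplement it. The shell note puts the diary first and lets weight supplement it.

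**5. Replacement denominator.** Weight used divided by (initial application amount x expected doses): (26 x 36)/(25.71 x 36) = 101.1%.

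**The case against.** The strongest reply is that Section 7.4 bases compliance on number of doses and points to Section 6.1.7, whose formula is sound when all tubes are returned. The footnote is only text under a shell, and weight is only a supplement. That stands. A reader might infer that the PP population would be emptied. The documents do not support this unless footnote [2] is what gets programmed.

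It can also be said that the 80%-120% rule is written for scheduled doses, not for a share of dispensed weight. That is true, but the shell classifies subjects under tube weight and offers no other threshold.

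The 72% ceiling is conditional. It needs all tubes returned and 50-g tubes. Footnote o of the double-blind schedule speaks of a 36-g tube, which would allow 36/36 = 100%, though still only 20/36 = 55.6% at 20 g. For these reasons, a reader who infers that reaching 80% by weight means exceeding the maximum application goes too far: missing tubes alone can produce it.

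Finally, expected doses run to the last day on study. A reader might pair 25.7 double-blind doses with 2 x 194/7 = 55.4 expected doses and conclude that a perfect double-blind subject scores 46%. Section 7.4 tabulates compliance by period, and the double-blind accountability shell stops at Day 90, so the plan does not produce that figure. Even on the long reading, a consistent numerator would include extension doses: 2 x 180/7 = 51.4, and 51.4/55.4 = 93%. What remains is a wording gap about period limits.

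**Conclusion.** The concern holds as a fault in the exposure table and an unresolved contradiction over the compliance flag. By weight, a fully adherent subject who returns all tubes scores at most 72%, and less with a smaller fixed amount, spare tubes or packaging weight. The tube-weight Compliant and Not Compliant rows therefore misclassify such subjects against the only threshold given. Footnote [2] yields zero or negative doses where Section 6.1.7 yields 101.1%.

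These figures assume 50-g tubes and full return; the packaging range is an assumption. The effect on PP and OLE PP is conditional: it arises only if the footnote is programmed or weight is allowed to override the dose count. Efficacy is analysed primarily in ITT and the PP repeat is labelled a sensitivity analysis, so the primary result does not depend on this. It should be fixed, but it does not threaten the main conclusion.

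**What to change.** 1. Correct footnote [2] of Table 14.1.5.3 to the Section 6.1.7 formula: tubes returned minus tubes returned unused.
2. Either divide weight used by (initial application amount x expected doses), both already derived in Section 6.1.7, or report tube weight descriptively and delete its Compliant and Not Compliant rows. If the first option is taken, note that the area-specific reductions and interruptions allowed in Section 3.4 lower the score of a subject who follows instructions, and that unreturned tubes raise it. Revise footnote [1] to match.
3. Name one measure for the PP and OLE PP flags in both Section 7.4 and the shell note: the Section 6.1.7 tube-count doses at 80%-120%. State that weight and diary do not override it, and remove the words that put a minimum in front of a range.
4. State that weeks on study and expected doses are counted within each period, double-blind and extension separately.
5. Reconcile the 36-g tube in footnote o of the double-blind schedule with the 50-g tubes stated elsewhere.

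The cost is SAP and shell wording. No new data are needed.
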